8.4.4 REPORTING OF PREGNANCY

While pregnancy itself is not considered an AE, pregnancy occurring in a clinical study must be followed to collect information regarding the experiences of gestation and pregnancy with study agent exposure. The investigator must report any pregnancy that occurs in a female study subject or female partner of a male subject subsequent to first exposure to the study agent until End of Study, or 3 months following a subject's last dose in the event of early termination. All pregnancies will be reported to the IRB/IEC, Sponsor, and CRO. In the event of a pregnancy, treatment will be discontinued, and the subject will undergo continued safety follow-up through pregnancy outcome.

Any pregnancy must be followed by the investigator until delivery or to the end of pregnancy. Any anomalies, complications, abnormal outcomes, or birth defect(s) observed in the child must be reported as an SAE within 24 hours of the investigator or study personnel's first knowledge.

8.5 STUDY HALTING RULES

If any of the following safety events occur, a Safety Evaluation Meeting (defined below) will be triggered:

- Three or more SAEs in the same SOC that are assessed as possibly or definitely related to the study agent by the investigator and confirmed as such by the Sponsor (see [Section 8.2.2 Relationship to Study Agent](#)).
- Within or between any of the dosing groups: an overall pattern of symptomatic, clinical, or laboratory events associated with the study agent that the Sponsor's Program Physician or designee consider a serious potential safety concern (e.g., suspicious overall pattern).

Events that are more likely related to the infusion procedure, such as infiltration or hematoma, will not be considered “drug related” and will not contribute to the count of definitely-related SAEs that would trigger a Safety Evaluation Meeting.

Safety Evaluation Meeting

If safety events of potential concern occur during the trial (i.e., 3 related events in the same SOC or a suspicious overall pattern, as defined above) a Safety Evaluation Meeting will be triggered, and dosing may be temporarily halted based on the observations. The Sponsor will inform investigators, FDA, ANSM, and TGA in the event of any temporary halt in dosing at any time during the conduct of the study. The purpose of the meeting is for investigators, the Sponsor, and the CRO Medical Monitor(s) to discuss and evaluate the safety of the subjects using available aggregated safety data and without compromising study blinding, unless the Sponsor deems unblinding necessary for safety evaluation.

Attendants at the Safety Evaluation Meeting will include the Program Physician of Alkahest (or his/her designee), the CRO medical monitor(s), and available active investigators participating in the trial. Such a meeting may also include external consultants with expertise relevant to the specific safety signal(s) detected. After sufficient data review, the Sponsor will choose one of the following courses of action:

1. Continue dosing with no change to protocol.
2. Halt dosing in all groups and stop the study.
3. Continue with a modified protocol design and amend the protocol as appropriate.

8.6 SAFETY OVERSIGHT

Safety oversight will be provided by the Sponsor’s Program Physician or his or her designee and the CRO’s Medical Monitor(s) in concert with the site investigators. There will be no formal Data Safety Monitoring Board (DSMB) established.

GRF6021 is

the primary objective of this study is to determine the safety and tolerability of GRF6021 in individuals with Parkinson’s disease, ongoing monitoring of cumulative safety data will be conducted in a systematic manner to ensure that any safety signals that may impact the overall benefit/risk ratio in this specific population will be detected, assessed, and any necessary action taken. Cumulative safety data (e.g., AE listings, vital sign plots, safety laboratory values, ECGs, physical exam results) will be reviewed by the CRO’s Medical Monitor(s) and by the Sponsor’s Program Physician throughout the study. If either physician detects any safety trends of concern, a Safety Evaluation Meeting will be convened as described in [Section 8.5](#) to assess the new safety signal(s).

The Sponsor’s Program Physician or designee is the final authority for safety oversight in the study.

9 CLINICAL MONITORING

Clinical site monitoring is conducted to ensure that the rights and well-being of human subjects are protected, that the reported trial data are accurate, complete, and verifiable, and that the conduct of the trial is in compliance with the currently approved protocol/amendment(s), with GCP, and with applicable regulatory requirement(s).

- Monitoring for this study will be performed by the study CRO in accordance with the Clinical Monitoring Plan (CMP).
- A mix of on-site and centralized monitoring will be performed to ensure the safety of clinical subjects and the accuracy and completeness of study data.
- The Sponsor will be provided with copies of monitoring reports per the timelines specified within the CMP.
- Details of clinical site monitoring tasks and scope are documented in the study's CMP. The CMP describes in detail who will conduct monitoring, at what frequency monitoring will be done, at what level of detail monitoring will be performed, and the distribution of monitoring reports.
- Independent audits may be conducted by the Sponsor in accordance with a quality oversight plan or equivalent to ensure monitoring practices are performed consistently across all participating sites and that monitors are following the CMP.

10 STATISTICAL CONSIDERATIONS

10.1 STATISTICAL DESIGN MODEL AND ANALYTICAL PLANS

A Statistical Analysis Plan (SAP) with analytical details and assumptions will be developed and finalized before database lock and unblinding of the study data.

10.2 STATISTICAL HYPOTHESES

Because the primary objective of the study is safety and tolerability, the study is not designed to detect statistically significant differences between active and placebo on efficacy endpoints. The statistical approach toward secondary efficacy endpoints will be primarily descriptive; within-subject changes from baseline for each dosing group and among-group differences will be evaluated.

10.3 ANALYSIS DATASETS

Four analysis datasets are possible; however, analyses may not necessarily be conducted with all four:

- **Intention-to-Treat (ITT) Dataset:** all randomized subjects.
- **Safety Dataset:** all subjects who received any amount of the study agent.
- **Evaluable Dataset:** all subjects who receive at least 5 of the 10 planned doses, have a diagnosis of PD and cognitive impairment per the inclusion criteria, and complete through Visit 8.
 - **Per Protocol Dataset:** a subset of the Evaluable Dataset. A detailed description of the reasons for exclusion from the Per Protocol population will be included in the Statistical Analysis Plan (SAP).

The presentation of baseline characteristics will be conducted on the ITT dataset. All safety analyses will be performed for the Safety Dataset. Analyses of the secondary endpoints will focus on the Evaluable and/or Per Protocol Datasets.

10.4 DESCRIPTION OF STATISTICAL METHODS

10.4.1 GENERAL APPROACH

Using the Evaluable and/or Per Protocol Datasets, all secondary endpoints will be summarized serially over time using descriptive statistics to assess the within-subject changes and between-group differences. Overall baseline and demographic data will be summarized using descriptive statistics; between-groups testing will be used to evaluate the effectiveness of the randomization in producing homogeneous pre-treatment groups.

For analysis of the primary and secondary endpoints, the following will be considered:

- For endpoints that are continuous in nature:
 - Number of observations, mean, median, minimum and maximum, and standard deviation (SD) values will be presented as descriptive summary
 - For inferential statistics:
 - If the Normality assumption is met, Paired t-test, or Analysis of Covariance (ANCOVA) using the baseline value as a covariate will be used
 - If the Normality assumption is not met, a rank –ANCOVA analysis i.e., an ANCOVA analysis on rank-transformed data or other non-parametric methods will be used
- For endpoints that are categorical in nature:
 - Frequency counts and percentages will be presented as descriptive summary
 - Chi-square test or Logit model will be used for inferential statistics

Subject disposition (e.g., the number of subjects randomized, completed, and discontinued) will be summarized, and medical history data will be listed. Prior and concomitant medications taken from screening and during the study will be categorized by World Health Organization classification for therapeutic class and drug name, listed and summarized by number and percentage of subjects.

Final analyses are not limited to the summaries described herein. As noted above, analytical details and assumptions will be fully presented in the SAP.

10.4.2 ANALYSIS OF THE PRIMARY ENDPOINT

Safety and tolerability will be evaluated by examining the occurrence of AEs, including Treatment-Emergent AEs and AEs leading to discontinuation from the study.

Summary tabulations of the reported adverse events will be presented by group after the verbatim terms have been coded to PTs and SOCs using the MedDRA Version 21.0 coding dictionary. The summaries will include severity and attribution to the study agent. Multiple reports of the same AE by the same subject will be counted only once at the highest severity and strongest attribution to the study agent.

The AE analyses will focus on those that are Treatment-Emergent, however any AEs that are reported after consent has been signed and prior to initial dosing will be tabulated as Intercurrent Events.

Additional details are presented in [Section 10.4.4](#).

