6.1.8 DURATION OF THERAPY

From screening to exit, the duration of study involvement for each subject and their trial partner is ~7 months.

All subjects will receive 5 consecutive days of therapy at the beginning of Weeks 1 and 13. Thus, the cumulative duration of therapy for all subjects will be 10 exposure days. The duration of therapy for a subject to be considered evaluable is 5 exposure days (see [Section 10.3 Analysis Datasets](#)).

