8.4 REPORTING PROCEDURES

8.4.1 ADVERSE EVENT REPORTING

All subjects who have given informed consent will be evaluated for AEs. All AEs that occur after the time of treatment with the study agent will be considered Treatment Emergent AEs. Subjects with Treatment-Emergent AEs must be followed until the AE is resolved or is stable, unless the subject is lost to follow up.

Each AE or suspected adverse reaction must be described as follows: the date of onset, date of resolution, severity (mild, moderate, severe), frequency of the event (single episode, intermittent, continuous), action taken with study treatment (no action taken, treatment held, treatment discontinued), outcome, causality* (unrelated, possibly related, definitely related), and seriousness criteria. Each AE or suspected adverse reaction must be recorded separately.

***Note:** Causality assessment will be made only when the AE occurs after the subject has initiated at least one infusion of the study agent. An AE occurring before the subject's exposure to study agent will always be labeled as "unrelated".

Any AE occurring during the study must be documented in the subject's medical records and as an AE in the CRF. Any SAE occurring during the study must be documented in the subject's medical records and as an SAE in the CRF.

A separate set of SAE pages should be used for each SAE. However, if at the time of initial reporting, multiple SAEs are present that are temporally and/or clinically related, they may be reported on the same SAE page.

The investigator should attempt to establish a diagnosis of the event (that meets the definition of an AE or SAE) based on signs, symptoms, and/or other clinical information. In such cases, the diagnosis should be documented as the AE and/or SAE and not the individual signs or symptoms. The diagnosis will become the basis for the verbatim term as reported by the investigator. If no diagnosis is known and clinical signs and symptoms are not present, the abnormal finding should be recorded.

In addition to the investigator's own description of the AE, each AE will be encoded according to the MedDRA.

The investigator will take all appropriate and necessary therapeutic measures required for resolution of the AE. Any medication necessary for the treatment of an AE must be recorded on the concomitant medication CRF.

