10.5 SAMPLE SIZE

A total of approximately 90 subjects will be randomized in a 2:1 ratio to active treatment (approximately 60 subjects) or placebo (approximately 30 subjects), with the intent of obtaining ~68 evaluable subjects who have received at least 5 doses and completed the study through Visit 8. Subjects who discontinue prior to completing Visit 8 may be replaced. Subjects who withdraw or are withdrawn during screening will be replaced.

The study is not statistically powered to detect differences in measures of clinical efficacy or biomarker endpoints. To evaluate potential safety signals, the statistical approximation described by Hanley (aka the “Rule of Threes” in which the upper bound of the 95% confidence interval for the frequency of an unreported AE is at most $3/n$ % where n represents the number of subjects who received active GRF6021 in the study) will be used. In a sample of 60 subjects, the upper bound of the 95% confidence interval for the frequency of an unobserved

AE is approximately 5%. In addition, the proposed sample size may be sufficient to identify trends in efficacy endpoints that will be used to determine the appropriate sample size for subsequent studies.

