9.1. Adverse Events

All AEs that occur after the time of treatment with the study agent will be considered TEAEs. Events meeting this definition will be those events that are a change from the subject's baseline conditions, including an increase in frequency or severity (these will be entered as new AEs). For AEs occurring on the date of first dose, if the time of onset is missing, the AE will be assumed to be treatment emergent.

All AEs, TEAEs, and SAEs will be coded using the MedDRA Version 20.1 or higher coding dictionary. The AE analyses will focus on those that are treatment emergent, however any AEs that are reported after consent has been signed and before initial dosing will be considered intercurrent events and flagged in the listings as such.

The causal relationship of the AE to the study drug is determined by the investigator as Unrelated, Possibly Related, or Definitely Related. These can be mapped to Unrelated (*Unrelated*) and Related (*Possibly Related* and *Definitely Related*). Adverse event summaries will be repeated for treatment related TEAEs.

Adverse events severity grades are reported as mild, moderate, or severe.

Summaries of incidence rates (frequencies and percentages) of individual TEAEs will be presented by SOC, PT, and treatment group. Such summaries will be displayed for all TEAEs, TEAEs by maximum severity, and TEAEs by relationship.

Each subject will be counted only once within each summation level (SOC and PT). If a subject experiences more than 1 TEAE within each summation level only, the TEAE with the strongest relationship or the maximum severity, as appropriate, will be included in the summaries of relationship and severity. If a particular event is missing the severity and/or relationship, then the strongest possible severity or relationship will be assumed for analysis (severity = severe, relationship = definitely related).

Incidences will be presented by descending frequency of SOC and PT within SOC, and then alphabetically within PT where the incidence is the same; this is based on overall subjects then alphabetically in case of a tie.

Missing and partially missing AE start and/or stop dates will be imputed, for the purpose of statistical analysis, according to the specifications described in Section 6.1.8.

In the AE data listings, all AEs will be displayed. AEs that are treatment emergent will be flagged.

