A test of hypothesis comparing the proportion of subjects reporting a TEAE throughout the study will be conducted using a Chi-square test or Fisher's exact test, as appropriate. The null hypothesis is that there is no difference in proportion between treatment groups, with a two-sided alternative that considers the possibility of a difference in either direction. The number and percentage of subjects reporting a TEAE and the 95% Wilson confidence interval (CI) for the proportion will be presented for each treatment group. In addition, the difference in proportions between the GRF6021 and placebo groups and the 95% Wilson CI will be presented. The same statistics and hypothesis testing will be performed for subjects reporting an SAE throughout the study.

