Note: Percentages are n/Number of subjects in the Safety Set*100. Subjects are summarized by treatment received. AEs were coded using MedDRA version 21.0. A TEAE is any AE that occurs after the time of treatment with the study agent. This will include any AE with onset prior to time of treatment with study agent and increased severity after the treatment administration. AESIs are TEAEs that are of special interest as defined by the protocol and are only recorded if the PI considers them as Adverse Events. If the reason for discontinuation entered on the study completion CRF was "Adverse Event" and the AE occurred between the start of the first infusion in Period 1 through the final infusion in Period 2, the derived action taken was set to 'study drug withdrawn' regardless of what was indicated on the CRF since treatment is administered during two distinct periods and not on a continuous basis.

[1] P value from Chi-square test.

[2] Related TEAEs are those marked as Possibly Related or Definitely Related on the CRF.

SOURCE: Listing 16.2.7.1

Programming note: If Fisher's exact test is used, update footnote [1] accordingly.

Table 14.3.1.2
Incidence of Treatment Emergent Adverse Events by SOC, PT, and Treatment
Safety Set

System Organ Class Preferred Term	Placebo (N=XX)	GRF6021 (N=XX)	Overall (N=XX)
Subjects with at least 1 TEAE	XX (XX.X%)	XX (XX.X%)	XX (XX.X%)
System Organ Class 1			
Preferred Term 1	XX (XX.X%)	XX (XX.X%)	XX (XX.X%)
Preferred Term 2	XX (XX.X%)	XX (XX.X%)	XX (XX.X%)
Preferred Term 3	XX (XX.X%)	XX (XX.X%)	XX (XX.X%)
System Organ Class 1			
Preferred Term 1	XX (XX.X%)	XX (XX.X%)	XX (XX.X%)
Preferred Term 2	XX (XX.X%)	XX (XX.X%)	XX (XX.X%)
Preferred Term 3	XX (XX.X%)	XX (XX.X%)	XX (XX.X%)

Abbreviations: PT = preferred term; SOC = system organ class; TEAE = treatment emergent adverse event.
 Note: Percentages are n/Number of subjects in the Safety Set*100. Subjects are summarized by treatment received.
 AEs were coded using MedDRA version 21.0. A TEAE is any AE that occurs after the time of treatment with the study agent. This will include any AE with onset prior to time of treatment with study agent and increased severity after the treatment administration. Subjects are counted once for each SOC and once for each PT. AEs are displayed by descending frequency of SOC, then PT within SOC, and then alphabetically by PT.
 SOURCE: Listing 16.2.7.1

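### The adverse event tables count subjects only, so a mild reaction that recurs across the 10 infusions prints the same as a single one

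*Protocol*

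**What the plan says.** The primary endpoint is the incidence of TEAEs and SAEs by MedDRA preferred term (PT) and system organ class (SOC). Three places set the counting rule:

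- Protocol 10.4.2: "Multiple reports of the same AE by the same subject will be counted only once at the highest severity and strongest attribution to the study".
- SAP 9.1: "Each subject will be counted only once within each summation level (SOC and PT").
- The SAP 14.2 shell for Table 14.3.1.2, which other incidence tables reuse: "Subjects are counted once for each SOC and once for each PT".

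Tables 14.3.1.1 to 14.3.1.4 and 14.3.2.1 to 14.3.2.4 hold n (%) of subjects. None has a column of events, a rate per infusion or a breakdown by infusion number. The only tested adverse event comparisons are in SAP 9.1: one "comparing the proportion of subjects reporting a TEAE throughout the study", and the same test for SAEs.

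On exposure, Protocol 6.1.8 says "the cumulative duration of therapy for all subjects will be 10 exposure days". On data, Protocol 8.4.1 requires each event to be recorded separately, with its "frequency of the event (single episode, intermittent, continuous"). No table or listing shell shows that item.

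**The concern.** The trial asks whether a regimen of two five-day courses of infusions is safe and tolerable. For such a regimen, the number of infusions that provoke a reaction is part of the answer, alongside the number of subjects who ever react. The planned tables report only the second. Maximum severity and strongest relationship do not restore the first, because a reaction that is mild every time is still shown once, as mild.

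A second effect concerns the tested comparison. With 10 exposures per subject, the proportion with at least one event can approach its ceiling in both arms if reactions are frequent. The two proportions then converge even where the burden per subject differs widely.

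**Working it through.** **The plan's own figure.** Protocol 10.5 gives an upper 95% bound of about 5% for an unobserved event in 60 active subjects. The rule of three gives 3/60 = 5.0%; the exact one-sided bound is 1 − 0.05^(1/60) = 4.87%. The figure reproduces. It concerns events never seen, so the counting rule does not touch it.

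**Inputs.** From Protocol 10.5, "approximately 90 subjects will be randomized in a 2:1 ratio to active treatment", so 60 active and 30 placebo. From Protocol 6.1.8, 10 infusions each. From SAP 4.1, two-sided tests at 0.05. The documents give no per-infusion reaction rate and no within-subject correlation; both are assumed below.

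**Recurrence.** Suppose 20% of each arm gets the same mild reaction, active subjects at all 10 infusions and placebo subjects once.

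- Planned table: 12/60 = 20.0% against 6/30 = 20.0%. Difference 0, Fisher p = 1.0.
- Events: 12 × 10 = 120 against 6 × 1 = 6.
- Per 100 infusions: 120/600 = 20 against 6/300 = 2.

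This illustrates what the table can show. It is not a forecast.

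**Loss of contrast.** If infusions are independent, the proportion of subjects with any event is 1 − (1 − p)^10, where p is the per-infusion risk. Power was simulated with 4,000 trials per scenario, binomial counts (or beta-binomial at correlation 0.2), comparing Fisher's test on any event with a Welch test on counts per subject.

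| Risk per infusion, placebo v active | Subjects with any event (independent) | Power, any event v counts (independent) | Power, any event v counts (correlation 0.2) |
|---|---|---|---|
| 2% v 4% | 18% v 34% | 28% v 43% | 14% v 28% |
| 5% v 10% | 40% v 65% | 58% v 80% | 35% v 42% |
| 10% v 20% | 65% v 89% | 74% v 98% | 61% v 68% |
| 20% v 40% | 89% v 99% | 56% v about 100% | 75% v 95% |
| 30% v 45% | 97% v 99.7% | 5% v 99% | 33% v 74% |

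A ceiling appears only from about 20% per infusion. The result also depends on the test. With chi-square or Fisher on any event against a rank test on counts, at correlation 0.2:

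- 5% v 10%: 44% power for each.
- 10% v 20%: 65% against 72% (48% against 52% at correlation 0.4).

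For the measure proposed below, each subject's share of affected infusions, at 20% v 40% and correlation 0.2, the planned test has 76% power and the share has 97%. If one event in five ends dosing, these become 76% and 93%.

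**The case against.** **The plan matches its endpoint.** Counting each subject once is the ordinary meaning of incidence. This stands in full. A reader might infer that the primary analysis is wrong; the documents do not support that. What is missing is a supplementary summary.

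**Saturation is not established.** A reader might infer that the comparison must saturate over 10 infusions. It need not. No reaction rate is given, and clustering within subjects weakens the ceiling: at 20% v 40% per infusion, subjects with any event are 84% v 98%, 68% v 92% and 53% v 80% at correlations 0.05, 0.2 and 0.4. Nor would a ceiling on any TEAE by itself affect the individual preferred-term rows. This stands, so the point is conditional. In the other direction, any TEAE also includes background events throughout follow-up, which the simulation leaves out.

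**Recurrence is partly visible.** A reader might infer that repeat reactions are never shown by arm. That is too strong. Table 14.3.2.4 splits blood-pressure events into those starting during and after each infusion period, and Table 14.3.6.1.2 gives blood pressures of special interest by visit and timepoint. Every adverse event is listed with treatment and start time. But the first table still counts subjects, the second counts readings rather than adverse events, and a listing is not a comparison.

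**Early stopping limits recurrence.** Appendix 11 recommends no further dosing after moderate-to-severe infusion events. Repeated reactions would therefore mainly be mild ones, for which the same appendix allows restarting. If such events never lead to withdrawal, the withdrawal table will not show them. Stopping does reduce the gain: comparing raw counts, with one event in five ending dosing, power is 74% for the planned test against 83% at 20% v 40% and correlation 0.2. The advantage of a per-infusion share is better kept (76% against 93%).

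**Conclusion.** The gap in the tables is certain and needs no assumed rate: outside the listings and the partial blood-pressure tables, no adverse event summary separates one reaction from ten. The loss of power is conditional. At an assumed 20% v 40% per infusion and correlation 0.2, it is 97 − 76 = 21 points against the share of affected infusions, or 93 − 76 = 17 points if one event in five ends dosing. At 5% v 10% there is little or no difference once reactions cluster within subjects, although a gap appears if infusions are independent (58% against 80%). At 10% v 20% the gain is modest unless that correlation is low. Adding the summary is a cheap improvement; the primary endpoint does not need correcting.

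**What to change.** Keep subject incidence as the primary summary, and make these changes in SAP 9.1 and the shells:

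1. Add an events column beside n (%) in Tables 14.3.1.2 to 14.3.1.4.
2. Add one supplementary table by arm. Numerator: infusions with at least one TEAE starting between infusion start and the end of that day's post-infusion monitoring. Denominator: infusions started. Express it per 100 infusions.
3. Compare arms on each subject's share of affected infusions, descriptively or by a Wilcoxon test. Present it beside infusions received and withdrawals due to adverse events, because a subject stopped after one reaction at the first infusion scores 1/1 = 100%, the same as one who reacts at all 10.
4. Show records marked intermittent separately, since one record can span several infusions, and add the frequency item to Listing 16.2.7.1.
5. State how infusion-day events without a start time are handled. SAP 6.1.8 sets a wholly missing time to 12:00 except on the first dosing day, which could move an event into or out of the window.

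The cost is SAP wording and a little programming. Event start times (Listing 16.2.7.1), infusion times (Listing 16.2.5) and the frequency item (Protocol 8.4.1) are already collected. The downside is a supplementary measure that early stopping and the same-day window partly limit: later-onset reactions fall outside it and appear only in the events column.
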